### 6.1.3 Statistical model

Changes from baseline to post-baseline visits in sTST will be analyzed using an MMRM with treatment (daridorexant 50 mg; placebo), period (TP I; TP II), week within period (Week 1; Week 2; Week 3; Week 4), the interaction of treatment and week as factors, and baseline sTST assessment as covariate.

An unstructured covariance matrix will be used to account for the correlation between repeated measurements from the same subject. This approach relies on the missing at random assumption. A restricted maximum likelihood approach in combination with the Newton Raphson Algorithm will be used to derive (unbiased) estimates of variance components. The Kenward-Roger approximation will be used to compute the denominator degrees of freedom and adjust standard errors [Kenward 1997]. If the analysis fails to converge, the following structures will be tested in the subsequent order until model-convergence is achieved: heterogeneous Toeplitz, Toeplitz, autoregressive, and compound symmetry.

To evaluate the efficacy hypotheses, appropriate contrasts will be used to test the treatment differences of interest (i.e., the difference in LS Mean change from baseline to Week 4 between daridorexant 50 mg and placebo).

The LS Mean for each treatment per time point will be displayed along with its associated standard error and 95% CI. For the daridorexant comparison with placebo, the placebo-adjusted LS Mean will be displayed along with the associated standard error, 95% CI and unadjusted 2-sided p-value. The null hypothesis will be rejected if the 95% CI for this difference excludes 0.

# 6.1.4 Handling of missing data

Section 6.1.1 explains how the primary efficacy endpoint is derived in the event of partially missing data.

The primary endpoint analysis will only include subjects with a valid baseline and at least one of the four weekly assessments for sTST, following the same approach as in the Phase 3 program [Mignot 2022]. Even though this does not fully follow the intent-to-treat principle, the approach seems justified as limited dropouts are expected (< 3%) due to the short duration of each treatment period (4 weeks) and the known safety and efficacy profile of daridorexant. Every effort will be made to keep all subjects in the study, even in the event of premature treatment discontinuation, to collect all the relevant data for analysis of the primary endpoint. Data collected after premature treatment discontinuation will be included in the primary analysis (following a 'treatment policy' strategy).

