	 b) Occurrence of suicidal ideation, suicidal behavior, and/or self-injurious behavior with/without suicidal intent based on the Columbia Suicide Severity Rating Scale[©] (C-SSRS[©])
	c) Morning sleepiness as determined by morning sleepiness VAS.
DESIGN	Multi-center, double-blind, randomized, placebo- controlled, 2-way cross-over, post-approval study.
	The study consists of 2 treatment periods (I and II) of 29 days each, separated by a 14–21 day washout period.
ENDPOINTS	 Primary efficacy endpoint Change from baseline to Week 4 in sTST in each treatment period

	Baseline is the mean value based on the screening sleep diary for sTST, which must be performed on each of the 7 days preceding Randomization.
	Week 4 is the mean value based on the sleep diary entries for sTST performed on study days 23–29 of each period.
	Other efficacy endpoints
	Other endpoints are listed in the main body of the protocol.
	Safety endpoints
	Safety monitoring will include:
	• Occurrence of treatment-emergent AEs up to 5 days after End-of-Treatment Period I (EOTP I) and/or End-of-Treatment Period II (EOTP II).
	• Occurrence of treatment-emergent AESIs up to 5 days after EOTP I and/or EOTP II.
	• Occurrence of treatment-emergent serious AEs up to 5 days after EOTP I and/or EOTP II.
	• Occurrence of treatment-emergent AEs leading to premature discontinuation of the study and/or treatment.
	• Change from baseline to EOTP I and EOTP II in vital signs (systolic blood pressure, diastolic blood pressure, and pulse rate).
	• Change from baseline to EOTP I and EOTP II in morning sleepiness as determined by the scores on the VAS in the morning.
	• Occurrence of suicidal ideation, suicidal behavior, and/or self-injurious behavior with / without suicidal intent based on the C-SSRS [©] at Visit 1, Visit 4, Visit 5, Visit 8, and Visit 9.
PERIODS	Screening period: Starts with the full signature of the informed consent form (ICF) at Visit 1 and lasts 14–21 days. All baseline assessments as well as eligibility checks will be done during this period.
	Treatment period (Periods I and II): Randomization will take place on Day 1 (Visit 2) after confirmation that all eligibility criteria have been met, prior to the first study drug

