9.2.2.2 Variable definition (sTST)

The change from Baseline^a to Week 4^b in sTST is calculated as follows:

Change from Baseline = Averaged value at Week 4 – Averaged value at Baseline.

^a Baseline is the mean value based on the screening sleep diary for sTST, performed on the 7 days preceding Randomization.

^b 'Week 4' is the mean value based on the sleep diary entries for sTST performed on study days 23–29 for each period. Data after the EOTP I/II visits will not be included in the analysis, as subjects are expected to be on double-blind treatment up to that point.

As sTST for Weeks 1–3 will also be included in the MMRM, definitions for the changes from baseline will be identical. For Week 1, sTST is averaged across days 2–8, for Week 2 across days 9–15, and for Week 3 across days 16–22.

Subjects must have at least 2 days of data during each week to calculate a weekly mean. Otherwise, the mean value will be considered missing for that week.

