## 4.1.4 Per-protocol set

The PPS includes all subjects from the FAS without important PDs occurring during the screening/baseline assessments or prior to Week 4 (in both treatment periods, i.e., between

Visit 2 and Visit 4 in TP I, and between Visit 6 and Visit 8 in TP II), which could affect the analysis of the primary endpoint variable.

The following important PDs will lead to exclusion from the PPS:

- At least one key inclusion criterion (except #1) was not met (#3, #4, #5, #6, #7; PD Code: 01A02);
- At least one key exclusion criterion was met (#3, #6, #7, #8, #13; PD Code: 01B01);
- Incorrect blister dispensed to the subject and at least one tablet was taken (PD Code: 02A01);
- Failure to comply with IMP storage/retention requirements impacting the quality of the IMP, reported as 'not to be used' by the Quality Assurance department, and at least one tablet was taken by the subject (PD Code: 02B01);
- At least one IMP compliance value < 80% (PD Code: 02E01);
- Non-compliance with blinding procedure/maintenance with consequences of patient treatment / study arm revealed or easily identifiable (PD Code: 03D01);
- Sleep diary not completed at least 2 days during Screening and Week 4 of each treatment period (PD Code: 03G02);
- Treatment with forbidden medication (PD Code: 04A01).

Study subjects will be evaluated according to the treatment they have been assigned to. If only one of the two treatment periods of a subject is affected by one of the above PDs, the subject still will be completely excluded from the analysis as the deviation also might have an impact on the second treatment period (e.g., forbidden medication with a long half-life or similar).

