### 10.4 Baseline

Baseline is the last non-missing assessment performed or value measured before or on the day of the first dose of any study treatment, unless otherwise defined in the specific analysis section.

Study subjects with no data for a given parameter before the first treatment administration will have a missing baseline (and missing change from baseline) for this parameter.

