## 13.2 SAS® code for mixed model for repeated measures

This model is used, for example, for the main analyses of the primary endpoint. Assuming the data are in 'long' format (i.e., one row for each subject/visit), example SAS® statements for the primary endpoint analysis are:

```
proc mixed data=data;
    class SUBJID TRT VIS PERIOD;
    model CHG = BASE TRT VIS PERIOD TRT*VIS / ddfm=kr;
    random int / subject=SUBJID;
    repeated VIS / subject=SUBJID*TRT type=un;
    lsmeans TRT*VIS / diff cl;
    estimate 'daridorexant 50 mg vs placebo at Week 4' TRT 1 -1 TRT*VIS 0 0 0 1 0 0 0 -1 / cl;

run;
```

The dataset 'data' includes baseline as well as changes (CHG) from baseline to Weeks 1, 2, 3, and 4 (VIS). Furthermore, TRT equals 1 and 2 for daridorexant 50 mg and placebo, respectively, and PERIOD equals 1 and 2 for TP I and TP II.

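### Subjects without a screening sTST baseline are dropped from the primary analysis, although in complete pairs that baseline cancels from the treatment contrast: a small, avoidable loss of precision

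*SAP*

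**What the plan says.** Entry to the primary analysis needs two things under SAP section 6.1.4: "The primary endpoint analysis will only include subjects with a valid baseline and at least one of the four weekly assessments for sTST". Protocol section 9.2.2.4 says the same. The SAP acknowledges the departure ("Even though this does not fully follow the intent-to-treat principle") and defends it by Phase 3 practice, expected dropout below 3%, short treatment periods and the known profile of the drug.

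The baseline is defined once, in Protocol section 9.2.2.2: "Baseline is the mean value based on the screening sleep diary for sTST, performed on the 7 days preceding Randomization". SAP section 6.1.1 uses it for both periods, and no Period II baseline is defined. In the example code (SAP section 13.2) change from baseline is the response and baseline is a covariate with a single slope: "model CHG = BASE TRT VIS PERIOD TRT*VIS / ddfm=kr". The covariance is a random subject intercept plus "repeated VIS / subject=SUBJID*TRT type=un". Under SAP section 10.4, a subject with no data before the first dose "will have a missing baseline (and missing change from baseline) for this parameter". Such a subject has no response in either period and leaves the model entirely.

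The SAP foresees randomized subjects with too few screening entries, because one of the per-protocol exclusions in section 4.1.4 is "Sleep diary not completed at least 2 days during Screening and Week 4 of each treatment period".

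**The concern.** In a cross-over the treatment effect is estimated mainly from within-subject differences. A subject with Week 4 means on both treatments has a fully observed difference whether or not the screening diary was kept, and the rule removes that subject all the same. None of the SAP's four reasons addresses this case: dropout, period length and drug profile concern data after randomization, and the Phase 3 precedent is cited without reference to the cross-over structure. At stake are some precision and the principle that all available FAS data enter the primary test.

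A second, smaller point is that the minimum number of diary days for a valid primary baseline is not written down. SAP section 6.1.1 sets a 2-day minimum for each week. Only the urine-night sensitivity analysis (section 6.1.6.2) and the IDSIQ derivation (section 6.3.3.5.1) extend it to baseline explicitly.

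**Working it through.** **1. The plan's own power.** Inputs from Protocol sections 1.1 and 9.4: SDs of change 42.5 and 50.5 min, correlation 0.58, stated SD of the difference 44 min, n = 50, two-sided alpha 0.05, differences of 26 and 20 min.

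SD of the difference = √(42.5² + 50.5² − 2 × 0.58 × 42.5 × 50.5) = √(1806.25 + 2550.25 − 2489.65) = √1866.85 = 43.2 min. The stated 44 is slightly conservative.

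Paired t-test power comes from the noncentral t distribution with n − 1 degrees of freedom and noncentrality δ√n/SD. With SD 44 and n = 50 it is 98.4% at 26 min and 88.3% at 20 min. Both stated figures (at least 90% and at least 80%) are reproduced.

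**2. Cancellation.** Write Y_D and Y_P for a subject's Week 4 means and B for the shared baseline.

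- Response: (Y_D − B) − (Y_P − B) = Y_D − Y_P.
- Covariate: the model has one slope β and no baseline-by-treatment term, so βB is the same in both periods and also drops out.
- Covariance: with a shared intercept and the same 4 × 4 block on each treatment (SAP section 13.2), a subject's between-treatment differences are uncorrelated with the sums. Baseline enters only the sums; in complete data the treatment contrast is estimated only from the differences.

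As a numerical check, one complete cross-over was simulated (50 subjects, sequences of 27 and 23, four weeks per period, the section 13.2 covariance held fixed). It was fitted by generalized least squares as change or raw sTST, each with and without baseline. All four fits gave the same Week 4 contrast (21.423) and the same SE (4.082). Dropping one complete subject raised the SE to 4.122, and dropping two raised it to 4.167.

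**3. Cost of the rule.** The documents give no rate of missing baselines, so the number lost is an assumption. SE = 44/√n.

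| Complete pairs lost | n | SE (min) | Power, 26 min | Power, 20 min |
|---|---|---|---|---|
| 0 | 50 | 6.22 | 98.4% | 88.3% |
| 1 | 49 | 6.29 | 98.2% | 87.6% |
| 2 | 48 | 6.35 | 98.0% | 87.0% |
| 3 | 47 | 6.42 | 97.7% | 86.2% |
| 5 | 45 | 6.56 | 97.2% | 84.7% |

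The smallest n that keeps 80% at 20 min is 40, so more than 10 of 50 pairs would have to go before that statement failed.

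**4. How many might be lost.** Assume the 2-of-7 rule applies to baseline and days are completed independently with probability p. Then P(fewer than 2 of 7) = (1 − p)⁷ + 7p(1 − p)⁶.

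- p = 0.8: 0.0000128 + 0.0003584 = 0.04%, or 0.02 of 50 subjects.
- p = 0.7: 0.4%, or 0.2 of 50.
- p = 0.6: 0.0016384 + 0.0172032 = 1.9%, or 0.9 of 50.
- p = 0.5: 8/128 = 6.3%, or 3.1 of 50.

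**The case against.** The strongest reply is that almost nobody will be affected. A subject needs only 2 diary days of 7, and step 4 shows that losing even one subject takes daily completion of about 60%. Clustered loss, such as a failed device, could still remove a subject, but the documents give no rate for it. This stands, and it settles the size of the point.

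The departure is also declared openly. The FAS rule on using all data allows specified exceptions, and section 6.1.4 is one. SAP section 6.1.5 will report missing sTST at baseline and allows further sensitivity analyses. Protocol section 10.6.1 has site staff review the completeness of subjects' entries. All of this is fair, but none of it keeps the affected subjects in the primary test.

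Baseline is not worthless either. It is needed for the per-treatment LS mean changes. Under an unrestricted covariance across both periods, or with incomplete pairs, it carries some information. Exact cancellation is a statement about complete pairs under the section 13.2 covariance with its parameters held fixed; REML estimation could move the SE slightly.

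Two stronger readings are tempting. From the synopsis wording, "which must be performed on each of the 7 days preceding Randomization", a reader might infer that a valid baseline needs all 7 days, so that many subjects would be lost and power would fall below the stated level. The documents do not support this. That wording tells subjects to keep the diary daily and sets no validity threshold; every stated minimum is 2 days (SAP sections 4.1.4, 6.1.1, 6.1.6.2 and 6.3.3.5.1), and nothing excludes a subject for 6 of 7. A reader might also infer selection bias. But the baseline diary is kept before randomization, so its absence cannot depend on the treatment sequence.

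**Conclusion.** The point holds as a minor one. The rule removes complete pairs whose treatment difference is fully observed, and the reasons given for it do not cover that case. The consequence is a small loss of precision and a needless departure from the FAS, with no bias in the comparison. With 1 to 3 of 50 subjects lost, the SE rises from 6.22 to between 6.29 and 6.42 min, and the stated power survives even with 5 lost. These figures rest on the plan's SD of 44 min, a paired t-test in place of the mixed model, and an assumed number of missing baselines.

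**What to change.** - **SAP section 6.1.4:** include every FAS subject with at least one weekly sTST mean. Fit weekly sTST as the response with baseline as covariate, and set a missing baseline to the overall baseline mean. Where every subject has a baseline, changing the response only shifts the baseline slope by 1, so the treatment contrast, SE and p-value are identical to those from change from baseline. For a complete pair the imputed value cancels as in step 2.
- **Per-treatment LS mean changes:** evaluate the LS means at the overall baseline mean and subtract that mean. The same constant comes off both treatments, so the estimand's difference of LS mean changes is unaffected.
- **SAP section 6.1.1:** state that the 2-day minimum also applies to the primary baseline mean.
- **SAP sections 11.1 and 13.2:** record the change, since Protocol section 9.2.2.4 carries the same rule, and update the example code.
- **Optional site check:** before randomization, confirm that enough baseline diary days exist. If they do not, Visit 2 has to move within the 14–21 day screening window, because baseline is the 7 days immediately before it and missed days cannot be filled in later.

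The cost is a few SAP sentences and one line of code, plus one line in the site checklist if the check is adopted. The change should be made before unblinding.

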# 6.1.5 Descriptive statistics

The primary efficacy endpoint (based on data used for the primary estimand) and its observed values (i.e., weekly averages of sTST) will be summarized over time by treatment using descriptive statistics.

A plot of the mean change from baseline over time for sTST will be provided by treatment (based on data used for the primary estimand).

The incidence and pattern of missing values will be explored to assess the appropriateness of the statistical analysis and the possible impact on the results (for the data used for the primary estimand). The incidence of missing data and the observed missing data patterns for the primary endpoint at baseline and each timepoint (Weeks 1, 2, 3, and 4) will be presented for each treatment. The missing data patterns will be sorted from completely missing to completely observed in the order of the first occurrence of missing data.

In addition, descriptive statistics will be provided by week and treatment, summarizing the number of available days that contribute to the weekly averages for sTST (for the data of the primary estimand). The analysis will be repeated by treatment period.

Based on the exploration of the observed missing data patterns, further sensitivity analyses in addition to those described below might be performed.

# 6.1.6 Sensitivity analyses

## 6.1.6.1 Per-protocol set

Page 21/50

The analyses of the primary endpoint will be repeated on the PPS (based on the same MMRM and data used for the primary estimand).

# 6.1.6.2 Analysis not considering the days of urine collection

As the collection of urine during pre-defined study nights might have an impact on the primary outcome sTST, a sensitivity analysis will be performed removing the days with urine collection from the weekly averages (based on data of the primary estimand).

For this analysis, 'Baseline' is defined as the mean value based on the screening sleep diary entries for sTST, completed for the 7 days preceding Randomization, except for the nights where urine was collected. 'Week 4' is defined as the mean value based on sleep diary entries for sTST completed for study days 23–29 for each period, except for the nights where urine was collected. As sTST for Weeks 1–3 will also be included in the MMRM, definitions for the changes from baseline will be identical. Subjects must have at least 2 days of data during each week to calculate a weekly mean (including baseline mean). Otherwise, the mean value will be considered missing for that week.

# **6.1.7** Supplementary analyses

No supplementary analyses are planned for this study.

## 6.1.8 Subgroup analyses

Subgroup analyses of the primary endpoint will be conducted by sex and country (based on the MMRM of the primary estimand and using data of the primary estimand).

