To evaluate the efficacy hypotheses, the difference in least squares mean change from baseline between daridorexant 50 mg and placebo at Week 4 will be estimated from the MMRM. An unstructured covariance matrix will be used to account for the correlation between repeated measurements from the same subject.

EU CT 2022-501246-30-00 Doc No D-23.307

Hypotheses for the primary endpoint are defined as follows: H₀: Mean of the within-subject changes in sTST from baseline to Week 4 between daridorexant 50 mg and placebo = 0H₁: Mean of the within-subject changes in sTST from baseline to Week 4 between daridorexant 50 mg and placebo $\neq 0$ Sample size estimation The assumptions for the sample size calculations were determined using data from studies ID-078A202 and ID-078A301 for the treatment groups daridorexant 50 mg and placebo. Data of sTST changes from baseline and the corresponding standard deviations (SDs) were derived based on simulations using sTST data at Baseline and at Month 1 from the ID-078A301 study for the age group ≥ 55 years. Subsets of 50 subjects were randomly selected from both the daridorexant 50 mg and placebo groups and compared via t-tests for independent samples, with means and SDs averaged across 1000 iterations. The simulations resulted in a mean difference of the change from baseline to Month 1 in sTST of 26 min for daridorexant 50 mg and placebo, with SDs of 42.5 min for placebo and 50.5 min for daridorexant 50 mg. Correlations between daridorexant 50 mg and placebo for sTST data were derived based on the cross-over study ID-078A202 (based on subjects aged ≥ 65 years). The Pearson correlation coefficient was estimated at 0.58. Combining all the information above resulted in an SD of the difference in the change of sTST from baseline to Month 1 of 44 min (based on the variance/covariance formula). Based on a two-sided type I error of 0.05, an estimated within-subject mean difference of the change from baseline to Month 1 in sTST between daridorexant 50 mg and placebo of 26 min and an associated SD of 44 min, a total sample size of 50 subjects, in this cross-over setting, provides at least 90% power, based on a two-sided paired

EU CT 2022-501246-30-00 Doc No D-23.307

Confidential

[figure not shown]
4 September 2023, page 27/122

t-test. A smaller within-subject mean difference between daridorexant 50 mg and placebo of 20 min would still result in a power of at least 80%.
--

Schema 1.2

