9.2.2.7 Subgroup analyses

No subgroup analyses are planned for this study because of the small study size. Some potential subgroup analyses might be added at a later stage and will be defined in the SAP.

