9.4 Sample size

The assumptions for the sample size calculations were determined using data from studies ID-078A202 and ID-078A301 for the treatment groups daridorexant 50 mg and placebo.

Data of sTST changes from baseline and the corresponding SDs were derived based on simulations using sTST data at Baseline and at Month 1 from the ID-078A301 study for the age group ≥ 55 years. Subsets of 50 subjects were randomly selected from both the daridorexant 50 mg and placebo groups and compared via t-tests for independent samples, with means and SDs averaged across 1000 iterations. The simulations resulted in a mean difference of the change from baseline to Month 1 in sTST of 26 min for daridorexant 50 mg.

Correlations between daridorexant 50 mg and placebo for sTST data were derived based on the cross-over study ID-078A202 (for subjects aged ≥ 65 years). The Pearson correlation coefficient was estimated at 0.58. Combining all the information above resulted in an SD of the difference in the change of sTST from baseline to Month 1 of 44 min (based on the variance/covariance formula).

Based on a two-sided type I error of 0.05, an estimated within subject mean difference of the change from baseline to Month 1 in sTST between daridorexant 50 mg and placebo of 26 min and an associated SD of 44 min, a total sample size of 50 subjects, in this cross-over setting, provides at least 90% power, based on a two-sided paired t-test. A smaller within subject mean difference between daridorexant 50 mg and placebo of 20 min still results in power of at least 80%.

9.4.1 Power considerations for the endpoint change from baseline to Week 4 in number of nocturnal voids assessed using a voiding diary

Sample size calculations/considerations for the endpoint change from baseline to Week 4 in number of nocturnal voids assessed using a voiding diary were performed based on two-sided paired t-tests for different scenarios:

- 1. Assuming a within-subject mean difference between daridorexant 50 mg and placebo in the number of nocturnal voids of 0.30 (averaged across 3 consecutive nights) after 4 weeks of treatment, and assuming an SD of the within-subject difference of 0.7, leads to approximately 80% power, based on 50 subjects and a type I error of 0.05, using a two-sided paired t-test.

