#### 6.3.3.3.1 Variable

As the study is mainly conducted in the Unites States, the derivation of the scores for EQ-5D-3L follows the publication by Shaw et al. [Shaw 2005]

Each of the 5-digit number combinations is assigned a score, e.g., for combination 11111 a score of 1.000 is assigned, while for combination 12332 a score of 0.302 is assigned. The assignments of all scores are summarized in Appendix 13.4.

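### The SAP adds subgroup analyses by sex and country using a primary MMRM with no treatment-by-subgroup term, so it gives separate group results but no comparison between groups.

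*SAP*

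**What the plan says.** Protocol 9.2.2.7 starts from "No subgroup analyses are planned for this study because of the small study size", then allows subgroup analyses to be added later and defined in the SAP. SAP 6.1.8 uses that allowance in one sentence: "Subgroup analyses of the primary endpoint will be conducted by sex and country (based on the MMRM of the primary estimand", on the primary estimand's data.

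The model it points to is in SAP 6.1.3, with example code in 13.2. The terms are baseline sTST, treatment, week, period and treatment by week. The covariance is unstructured over weeks, and the code adds a random subject intercept. The reported output includes a 95% CI and an unadjusted two-sided p-value for the treatment difference. If the fit does not converge, SAP 6.1.3 steps through four simpler covariance structures.

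SAP 6.1.8 gives no between-group contrast, minimum group size, rule for pooling countries or statement that the results are descriptive. SAP 11.1 reports no changes from the protocol's analyses, and 11.4, which lists additions, omits this one.

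SAP section 2 names the United States, Spain and Germany. On country balance, the only information is in SAP 6.3.3.3.1: "As the study is mainly conducted in the Unites States". Randomization is not stratified (protocol 6.1.4).

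**The concern.** A subgroup analysis asks whether the treatment effect differs between groups. Separate fits do not answer that. They invite a comparison of significance labels, and in groups of this size the labels will often disagree when the true effects are identical. A clinical study report could then show an apparent benefit in one sex or country and not in another, with nothing in the output to show that the difference is compatible with chance.

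Country adds a second problem. About 50 subjects are spread over three countries, mostly in one, so a separate fit in each of the other two may have very little data behind it.

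**Working it through.** **Inputs.** Protocol 9.4 gives "Based on a two-sided type I error of 0.05", a difference of "26 min and an associated SD of 44 min", 20 min as the smaller effect, a correlation of 0.58 and 50 subjects. The synopsis gives the arm SDs: "with SDs of 42.5 min for placebo and 50.5 min for daridorexant 50 mg". Sex and country splits are not in the documents, so a range is assumed.

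**Step 1: the plan's own figures.** SD of the within-subject difference = √(42.5² + 50.5² − 2 × 0.58 × 42.5 × 50.5) = √1866.85 = 43.2 min; the plan uses 44. Exact paired t-test power (noncentral t, n − 1 df) at n = 50 and SD 44 is 98.4% for 26 min and 88.3% for 20 min. The statement "a total sample size of 50 subjects, in this cross-over setting, provides at least 90% power, based on a two-sided paired t-test" therefore holds as a lower bound, as does the claim of at least 80% at 20 min.

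**Step 2: two sexes with the same true effect.** Power p₁ and p₂ come from the same formula within each sex. The chance that exactly one is significant is p₁(1 − p₂) + p₂(1 − p₁). For 25/25 at 26 min this is 2 × 0.809 × 0.191 = 0.309.

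| Assumed split | Power, 26 min | Exactly one significant | Power, 20 min | Exactly one significant |
|---|---|---|---|---|
| 25/25 | 81% / 81% | 31% | 59% / 59% | 48% |
| 30/20 | 88% / 71% | 34% | 67% / 49% | 50% |
| 35/15 | 92% / 57% | 44% | 74% / 37% | 56% |
| 40/10 | 95% / 39% | 60% | 80% / 25% | 65% |

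A two-sided 0.05 test of the difference between sexes would call equal effects different about 5% of the time.

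**Step 3: three countries with the same true effect.** The chance that the three verdicts do not all agree is 1 − Πp − Π(1 − p). At 26 min it is 71% (17/17/16), 82% (30/10/10) and 94% (40/5/5). At 20 min it is 73%, 77% and 83%.

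**Step 4: precision in a small country.** The 95% CI half-width is t(n − 1) × 44/√n:
- n = 10: 2.262 × 13.91 = 31 min
- n = 8: 2.365 × 15.56 = 37 min
- n = 5: 2.776 × 19.68 = 55 min

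**Step 5: can the model be fitted?** Fixed effects: 1 intercept + 1 baseline + 1 treatment + 3 week + 1 period + 3 treatment by week = 10. Covariance: 10 unstructured + 1 random intercept = 11. The SAP 13.2 model was fitted to 60 simulated data sets per size, with complete data, balanced sequences and an assumed within-period week correlation of 0.6. The unstructured fit was singular or unbounded in 100% of runs at n = 2 and 3, 88% at n = 4, 58% at n = 5, 3% at n = 6 and 0% at n = 8 or more.

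Separately, the chance that all of a country's subjects fall in one sequence, which confounds treatment with period, is about 23–25% at n = 3, 5–6% at n = 5 and below 0.2% at n = 10.

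**Step 6: what a proper contrast would offer.** For 25/25, the SE of the difference between sexes is 44 × √(2/25) = 12.4 min and the 95% CI half-width is 2.011 × 12.4 = 25 min. The difference detectable with 80% power is about 35 min.

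**The case against.** The SAP attaches no hypothesis, consistency claim or decision rule to sex or country. The only null hypothesis is the overall Week 4 difference, so the discordance figures measure what a reader might wrongly infer and not an error in the planned estimates. SAP 6.1.8 does not literally say that the model is refitted in each group, and the code in 13.2 is an example for the primary analysis, where subgroup terms would not be expected. A proper contrast would also be imprecise.

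Most of this stands, but it does not remove the point. The named model has no subgroup term and its standard output carries a p-value, so separate fits are what a programmer would most naturally produce. An imprecise contrast at least shows how little the data can say.

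Three stronger readings are tempting, and the documents do not support them.

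- A reader might infer that the country groups cannot support the model. No subject numbers per country are given, the simulated fits were estimable at 8 or more subjects, and the fallback in SAP 6.1.3 addresses non-convergence. It does not cure imprecision or a country with only one sequence.
- A reader might infer that adding subgroups breaches the protocol. Protocol 9.2.2.7 expressly allows it.
- A reader might infer that the primary type I error is affected. It is not, because these analyses lie outside the testing strategy.

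**Conclusion.** The point holds as a weakness in how the subgroup analyses are specified. As written they give per-group verdicts and no between-group comparison. With identical true effects, the two sexes would receive different significance labels in 31–60% of trials at 26 min and 48–65% at 20 min. These figures rest on the plan's SD of 44 min, a paired t-test standing in for the MMRM contrast, and assumed splits from 25/25 to 40/10.

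For country the conclusion is conditional on counts that the documents do not give. Separate unstructured fits may fail at about 5 or fewer subjects, a threshold that depends on the simulation's assumptions. At 8 to 10 subjects the half-width of about 31–37 min exceeds the 26 min design effect. The omission from SAP 11.4 is a smaller documentation gap.

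**What to change.** For each factor, fit one MMRM on all subjects that adds subgroup, treatment by subgroup, subgroup by week, and treatment by subgroup by week to the primary model, with a common covariance. Report the Week 4 treatment effect in each subgroup and the difference between subgroups, each with a 95% CI, and label the analysis descriptive. State in advance how countries too small to estimate alone will be pooled; the United States against the two European countries is one option. Leaving out within-group p-values would also help, but that is a matter of preference. List the analysis in SAP 11.4.

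The cost is a few lines of SAP text and one model per factor. The model assumes the same covariance in every subgroup, and the contrast remains imprecise, at about ±25 min for an even sex split.
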